### **Study Visit 8 (Day 14) – to occur within a +5 day window (D14 to D19)**

Fourteen (14) days after RV inoculation, subjects will return to complete the ACT questionnaire and to report any adverse events. In addition, a limited physical examination will be performed including chest auscultation and a final assessment of FeNO (asthmatics only)/spirometry will be performed. A repeat CBC & differential (3ml purple top) will be drawn if ANC or ALC fell below 500/ $\mu$ L Day 4. If subject is still symptomatic they will be contacted at day 21 with the possibility of an unscheduled visit.

### **Study Visit 9 (Day 21)**

The Day 21 visit will only occur for subjects who remain symptomatic at Day 14 or whose ANC or ALC falls below 500/ $\mu$ L at Day 4 without recovery by Day 14. This visit will occur by phone except in cases where a repeat CBC & differential is needed to check ANC and ALC counts. Participants will be asked if they continue to have symptoms, and whether or not they have had any new or worsening symptoms/conditions since Day 14. If either of these questions is answered affirmatively, the PI will be contacted, and an unscheduled visit will be arranged if the PI feels it is warranted.

### **8.3. Unscheduled Visits**

If disease activity increases after day 7 or other concerns arise either between visits 6 and 7 or after visit 8, participants will be instructed to contact study personnel and may be asked to return to the study site for an “unscheduled” visit. Unscheduled visits will include a physical exam, interim medical history, recording of adverse events and medications, and spirometry testing. Diary cards will also be collected as applicable.

### **8.4. Visit Windows**

Study visits should take place within the time limits specified below. Visit 1 screening/baseline visit will take place between 5 days and 28 days prior to scheduled inoculation. Post-inoculation visits will only take place on the specific day with the exception of visit 7, which will be permitted to have a  $\pm$ 24 hr window, and visit 8, which will have a +5 day window.

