### 3. Study Design

#### 3.1. Description of Study Design

A total of 60 subjects will be enrolled in this open label challenge study over a period of 48-54 months (September 2016 – March 2021). These will include 20 subjects in each of 3 cohorts: healthy controls, allergic rhinitis controls, and asthmatics. At Visit 1 subjects will have baseline assessments of lung function and blood work. Viral inoculation will be performed on day 0 and assessments of cold and allergy symptoms, nasal viral titers, nasal mediators, lung function, and FeNO will be obtained on days 0 and days 1, 2, 3, 4, and 7 post-infection (dpi). In addition, methacholine challenges (days -7 and 4) will be performed. Finally, nasal biopsies will be performed on day 4 to assess extent of viral infection and nature of cell death (apoptosis v. necrosis). Each subject will complete the study at day 14.

Table I: Study Outline\*\*\*

Visit #:	1	2	3	4	5	6	7	8	9
	Day -7	Day 0	Day 1	Day 2	Day 3	Day 4	Day 7	Day 14**	Day 21
Symptom Assessment	X	X	X	X	X	X	X	X	X
Negative CoVID19 screen (afebrile/preserved sense of smell)	X	X	X	X	X	X	X	X	X
Pregnancy Test	X	X				X	X		
Viral antibody serology/CBC	X								
Virus inoculation		X							
Viral titers		X	X	X	X	X	X		
FEV1/ FeNO	X	X	X	X	X	X	X	X	
Nasal Scraping		X	X	X	X	X	X		
Nasal Washes / Sponge		X	X	X	X	X	X		
Nasal Biopsy						X			
Blood for Th immune deviation / AEC	X					X			
Methacholine Challenge	X					X			

\*\*\* If subject is still symptomatic at day 14 they will be contacted at day 21 with the possibility of an unscheduled visit. A Day 21 in-person visit will be scheduled if ANC or ALC falls below 500/ $\mu$ L, and does not return to baseline following the Day 14 blood draw. If disease activity increases after day 7 or other concerns arise either between visits 6 and 7 or after visit 8, participants will be instructed to contact study personnel and may be asked to return to the study site for an "unscheduled" visit.

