### **8.2. Visit 1 – Screening/Baseline Visit (Day -7)**

Participants considered for study will have previously participated in the screening protocol within 1 year before Visit 1. Clinical information obtained from the screening protocol may be applied to eligibility as described in Section 4 above, and will be added to the participants' Visit 1 study record.

For this study, all visits will take place at the Clinical Research Unit on the 1st floor of the Medical Center Barringer Wing or at the University Hospital or the Clinical Research Center (CRC) located on the 3rd floor of the University of Virginia Children's Hospital Outpatient Building (Battle Building) in Charlottesville. The baseline visit will take place ~7 days (5-28 days) before RV inoculation visit. The research study will be explained in lay terms to each potential research participant. The potential participant will sign an informed consent form before undergoing any study procedures. Once the informed consent has been signed, the participant is considered enrolled in the (screening) study and will be assigned a unique participant number

The purpose of the baseline visit is to reconfirm eligibility to continue in the study and to perform baseline assessments.

The following procedures, assessments, and laboratory measures will be conducted to confirm participant eligibility and for baseline assessments:

1. Urine pregnancy test for all women of childbearing potential.
2. ACT (asthmatic subjects) – must be  $\geq 20$
3. Blood (10 ml) for viral antibody serology and CBC & differential and 50-ml of blood will be obtained for PBMCs (which can be collected at Visit 2 as long as collection is before inoculation).
4. Spirometry
5. Exhaled nitric oxide (FeNO) on asthmatics only
6. Subjects will be instructed on the use of diary cards, which will be used to record upper and lower respiratory tract symptom scores twice daily, as well as how to use the ATS approved Microlife Electronic PEF and FEV1 monitor and the number of puffs of albuterol required for resolution of symptoms.
7. If required, subjects will also be given an albuterol inhaler (MDI) to use as a rescue medicine as needed.
8. Baseline assessment of past medical history. An additional targeted medical history of acute events over the last month will be obtained to use in our assessment of adverse events.
9. A limited physical examination will be performed including chest auscultation.

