### **Study Visit 2 - Inoculation (Day 0)**

1. Urine pregnancy test for all women of childbearing potential.
2. Vital Signs (blood pressure, heart rate, temperature, height, weight)
3. Prior to inoculation asthma control will be confirmed by the following means -
  - a. Diary cards will be reviewed
  - b. AEs review
  - c. Spirometry – Must demonstrate normal lung function (FEV1 > 70% predicted or FEV1/FVC ratio > 75% for subjects with FVC values between 80 and 87% predicted whose FEV1 values fall below 70%).
  - d. A limited physical examination will be performed including chest auscultation
4. Nasal scraping
5. Nasal wash / sponge

6. Blood draw – 50mls of blood will be obtained for PBMCs ONLY if not collected at Visit 1
7. Exhaled nitric oxide (FeNO) on asthmatics only
8. Inoculation of subjects with RV-16

Continued eligibility must be confirmed during the initial part of this study visit. Sample collection and the inoculation may be delayed if a subject is ill or has evidence of loss of asthma control. The inoculation will not occur if the upper airway modified Jackson criteria symptom scores are  $\geq 7$ . The participant may be brought back to continue the Day 0 visit. Procedures completed may be repeated to confirm the subject's eligibility. The repeat visit must occur within the stated visit window from Visit 1.

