### **Study Visit 6 (Day 4)**

1. Urine pregnancy test for all women of childbearing potential.
2. Diary cards will be reviewed for symptom control and AEs.
3. A limited physical examination will be performed including chest auscultation and temperature
4. Nasal scraping
5. Nasal wash / sponge
6. Spirometry
7. Exhaled nitric oxide (FeNO) on asthmatics only
8. Blood sample (50-ml) will be obtained for AEC (part of the CBC & differential) and for collection of PBMCs for later assessment of Th2-immune deviating capacity of nasal secretions.
9. Nasal biopsies will be obtained
10. Methacholine Challenge

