**Units of analysis:** The day 0  $\log_e$ (IL-25 qPCR expression) measurements will be subtracted from the post-challenge day 1, 2, 3, 4, and 7  $\log_e$ (IL-25 qPCR expression) measurements and these *subject-specific* pre- versus post-challenge changes in  $\log_e$ (IL-25 qPCR expression) will be the units of analysis. **Analytical approach:** The changes in  $\log_e$ (IL-25 qPCR expression) on post-challenge days 1, 2, 3, 4, and 7 will be analyzed as repeated measures by way of a linear mixed model (LMM). **LMM fixed effects:** Two sources of variability in the pre- versus post-challenge changes in  $\log_e$ (IL-25 qPCR expression) will be of primary interest. One source of variability will be the study-group to study-group variability (i.e. asthmatics, allergic rhinitis controls, and healthy-controls) in the changes in  $\log_e$ (IL-25 qPCR expression), while the other source of variability will be the post-challenge day to day variability in the changes in  $\log_e$ (IL-25 qPCR expression). **Concomitant variable variability:** Variability in the  $\log_e$ (IL-25 qPCR expression) changes due to inherent differences in day 0  $\log_e$ (IL-25 qPCR expression) will be extracted from the residual error to increase statistical power. **Random effects:** *Subject-specific* and *time-specific* random effects will be incorporated into the LMM to allow *intra-subject* measurement correlation to be accounted for in variance estimation and hypothesis testing. **Hypothesis testing:** *Between-study-group comparisons:* With regard to hypothesis testing, the pivotal comparisons will be the *between* study-group comparisons of the mean changes in  $\log_e$ (IL-25 qPCR expression) on post-challenge study days 3 and 4 when cold symptoms are expected to peak. More specifically, we will compare if the study-day 3 and study-day 4 mean changes in  $\log_e$ (IL-25 qPCR expression) differ between the 3 different underlying study-populations after taking into account the inherent variability in challenge study-day 0  $\log_e$ (IL-25 qPCR expression). These comparisons will require conducting a total of 6 hypothesis tests (i.e. 3 per study day), and in order to maintain an *intraday* experimental-type I error rate of 0.05, the null hypothesis rejection rule for the “*intraday*” *between-group* comparisons will be based on a Bonferroni corrected two-sided  $p \leq 0.0167$  (i.e.  $0.05/3$ ) rejection rule. *Within-study-group comparisons:* On a per *study-group* basis, we will conduct statistical tests to determine if the means of the  $\log_e$ (IL-25 qPCR expression) distributions on post-challenge days 1, 2, 3, 4, and 7, differ from the mean of the  $\log_e$ (cytokine expression) distribution on challenge study day 0. The *within-study-group* comparisons will be considered *secondary* in nature, and this set of comparisons will be primarily focused on the challenge study-day 3 and challenge study-day 4 changes in mean  $\log_e$ (IL-25 qPCR expression) when symptoms are expected to peak. More specifically, we will test if the mean of the  $\log_e$ (IL-25 qPCR expression) distribution is the same on challenge study-day 0 and challenge study-day 3 and if the mean of the  $\log_e$ (IL-25 qPCR expression) distribution is the same on challenge study-day 0 and challenge study-day 4. A Bonferroni corrected two-sided  $p \leq 0.025$  (i.e.  $0.05/2$ ) decision rule will be utilized as the null hypothesis rejection criterion for this set of tests. **Confidence intervals:** To aid in data interpretation, a 95% confidence interval will be constructed for each *between-group* comparison and for each *within-group* comparison. **Scale of interpretation:** The point-estimate and the lower and the upper 95% confidence interval limits will be anti-log transformed so that point-estimate and the lower and the upper limits of the 95% confidence interval represent ratios of geometric mean cytokine expression. **Alternative analytical approach:** If the linear mixed model assumptions are deemed to be violated for this endpoint, we will use a linear mixed model based permutation test strategy to derive empirical based *distribution free* tests for testing the aforementioned *between-group* and *within-group* hypotheses.

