***Analysis of circulating eosinophil count:*** Changes in the absolute eosinophil count (AEC) from day -7 to post-challenge day 4 will be compared between the 3 different groups via ANOVA. ***Model specification:*** The primary source of  $\Delta$  AEC variation that will be examined will be the variation due to study-group to study-group variation. ***Hypothesis testing:*** We will test if the 3 underlying study-population  $\Delta$  AEC distributions share the same mean. A  $p \leq 0.05$  decision rule will be utilized as the null hypothesis rejection rule for this test. If rejected a Bonferroni corrected two-sided  $p \leq 0.05/3$  decision rule will be utilized as the null hypothesis rejection rule for between-group comparisons. ***Alternative analytical approach:*** If the ANOVA model assumptions are violated, the  $\Delta$  %EC data will be analyzed by *distribution-free* permutation methods.

***Analysis of eosinophil percent of total cells:*** Changes in the eosinophil percent of total cells ( $\Delta$  %EC) from day -7 to post-challenge day 4 will be compared between the 3 different groups via ANOVA. ***Model specification:*** The primary source of  $\Delta$  %EC variation that will be examined will be the variation due to study-group to study-group variation. ***Hypothesis testing:*** We will test if the 3 underlying study-population  $\Delta$  %EC distributions share the same mean. A  $p \leq 0.05$  decision rule will be utilized as the null hypothesis rejection rule for this test. If rejected a Bonferroni corrected two-sided  $p \leq 0.05/3$  decision rule will be utilized as the null hypothesis rejection rule for between-group comparisons. ***Alternative analytical approach:*** If the ANOVA model assumptions are violated, the  $\Delta$  %EC data will be analyzed by *distribution-free* permutation methods.

***Analysis of upper respiratory symptom scores:*** The upper respiratory symptom scores that will be reported daily from challenge study day 0 to challenge study day 7, will be analyzed in two ways. In the first approach, cumulative upper respiratory total symptom (CURTS) will be computed for challenge days 0 to 4, and for challenge days 0 to 7. In the second approach the daily total upper respiratory symptom scores will be analyzed. *Please see the analytical plan for the analysis lower respiratory symptom scores for further details (section 13.4.2).*

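### The eosinophil change scores start from a count taken 5 to 28 days before inoculation, not at day 0, so drift before the virus could mimic or mask an RV effect on this secondary outcome

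*Combined protocol and SAP*

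**What the plan says.** **Analysis.** Section 13.4.4 states: "Changes in the absolute eosinophil count (AEC) from day -7 to post-challenge day 4 will be compared between the 3 different groups via ANOVA". Eosinophil percent of total cells is handled in the same way over the same interval. Study group is the only factor named in either ANOVA.

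**Sampling.** In Table I (section 3.1) the row "Blood for Th immune deviation / AEC" is marked at Day -7 and Day 4 only. The Day 4 visit list confirms the second draw: blood "will be obtained for AEC (part of the CBC & differential").

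**Timing of the baseline.** Day -7 is a nominal label. Under section 8.4, "Visit 1 screening/baseline visit will take place between 5 days and 28 days prior to scheduled inoculation". Section 8.2 gives the same range and lets Visit 1 be spread over several visits inside the window.

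**Day 0.** The Visit 2 list has no CBC. Its only blood draw is conditional: "50mls of blood will be obtained for PBMCs ONLY if not collected at Visit 1". The matching allowance in section 8.2, "which can be collected at Visit 2 as long as collection is before inoculation", concerns the PBMC sample, as the Visit 2 list shows.

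**Other change scores.** For IL-25 in section 13.4.2, the day 0 log values are the baseline; these "measurements will be subtracted from the post-challenge day 1, 2, 3, 4, and 7" log values. Section 13.4.4 also uses day 0 for IL-33, TSLP, the interferons and IL-15, FEV1 and, through the FEV1 specification, FeNO. Those models adjust for the baseline value.

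**The concern.** The difference between Visit 1 and day 4 is read as a response to RV, but part of it may have arisen before any virus was given. The expression, FEV1 and FeNO endpoints avoid this by starting on the day of inoculation, and the documents give no reason for treating eosinophils differently.

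The cohorts are defined by disease and not randomised, so nothing balances pre-inoculation change between them. Eosinophil counts in sensitised subjects may follow allergen exposure in a way that those of non-allergic controls do not; this is an assumption, not something the documents show. The overview in section 13.1 predicts a systemic rise in eosinophils in asthma and AR. Upward drift confined to those cohorts would look like that prediction, and downward drift would conceal a true rise. The count is taken only once after challenge, so the time course cannot separate the two explanations.

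**Working it through.** The plan states no SD, detectable difference or power for the eosinophil change, so there is no figure of its own to reproduce.

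**1. Share of the interval before the virus.** Let L be the lead from Visit 1 to inoculation: 5 to 28 days (sections 8.2 and 8.4), nominally 7. The day 4 visit has no window (section 8.4), so the interval is L + 4 days and the pre-virus share is L/(L + 4).

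| L (days) | Interval (days) | Pre-virus share |
|---|---|---|
| 5 | 9 | 5/9 = 55.6% |
| 7 | 11 | 7/11 = 63.6% |
| 28 | 32 | 28/32 = 87.5% |

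The share exceeds half at every permitted lead. With a day 0 baseline it is 0/4 = 0.

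**2. How much drift a day 0 baseline would remove.** If drift were constant per day (assumption), the drift left in the change score would be 4/(L + 4) of the present amount: 4/9 = 44%, 4/11 = 36% and 4/32 = 12.5% for leads of 5, 7 and 28 days.

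**3. Illustration of the effect on the planned test.** Inputs from the plan: 20 per group, global ANOVA at 0.05, then pairwise tests at 0.05/3. Assumptions: no RV effect, and the same upward drift of d SDs of the change score in both allergic cohorts, with none in controls. The group means are 0, d and d, so the noncentrality is 20 × (2/3)d², and the global rejection probability comes from the noncentral F with 2 and 57 df. The last column comes from 40,000 simulated trials that apply the global test and then the pairwise tests.

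| d (SD) | Noncentrality | Global test rejects | Both allergic cohorts declared above control |
|---|---|---|---|
| 0 | 0 | 5.0% | 0.1% |
| 0.25 | 0.83 | 11.4% | 1.3% |
| 0.5 | 3.33 | 33.7% | 8.7% |
| 0.75 | 7.50 | 66.3% | 30.9% |
| 1.0 | 13.33 | 90.0% | 63.2% |

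If only the asthma cohort drifts, the global test rejects about as often, but both allergic cohorts are declared above control in under 1% of simulated trials at every d shown.

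**4. Drift that varies between subjects.** Zero-mean subject-level drift in the allergic cohorts left the simulated ANOVA type I error at 0.050 to 0.052. Its cost is precision: the variance of the change is increased by the variance of the drift.

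Steps 3 and 4 show how the test responds to drift. They do not say how much drift this trial has.

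**The case against.** The strongest reply is that bias needs a coordinated shift that nobody has shown. Enrolment runs over 48 to 54 months, and allergic subjects qualify on any one positive test to an inhalant panel, so calendar dates and relevant allergens differ between subjects. Drift in different directions adds variance rather than a mean difference. Drift common to all three groups cancels, and drift common to asthma and AR cancels in that contrast. All of this stands.

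There is also some protection. Section 1.3 describes the group's challenges as done outside periods of increased allergen exposure. Subjects with a respiratory infection in the previous 2 months are excluded, inoculation is barred at an upper-airway score of 7 or more, and it may be delayed for illness or loss of asthma control. These reduce drift. However, the off-season practice is not written as an eligibility or scheduling rule in this protocol, and a delayed inoculation lengthens the lead within the permitted window.

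A reader might infer that drift in the allergic cohorts does produce the predicted eosinophil result, or that 56% to 88% of the observed change is not due to the virus. The documents support neither. They give no drift, no direction and no SD, and days elapsed are not units of bias. High false-positive rates for one pairwise test, obtained by assuming a uniform drift in one cohort, would not show imitation of the prediction either, because the prediction concerns two cohorts.

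Methacholine PD20, in the same secondary outcome, is also analysed from day -7, and section 8.2 accepts a result up to a year old. That is a separate matter, which the change proposed here does not address.

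**Conclusion.** The point holds as a weakness in the baseline of two eosinophil analyses. Both change scores start 5 to 28 days before inoculation, so more than half of the interval always precedes the virus, and the ANOVA has no term for baseline value or lead time. Differential drift before inoculation could mimic or mask an RV effect, and drift that varies between subjects costs precision.

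The lead times and shares follow directly from the documents. The size and direction of any bias do not, and the table of rejection rates rests wholly on assumed drift. The reach is limited to one of three markers in secondary outcome 4 and the related eosinophil-percent analysis. No primary endpoint or power calculation uses either change score. The change is worth making because the remedy is small and the count is the direct test of the systemic eosinophilia that the plan predicts.

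**What to change.** - Add a CBC with differential at Visit 2, drawn before inoculation, to Table I and the Visit 2 list.
- In section 13.4.4, define the changes in absolute count and in eosinophil percent as day 4 versus day 0. Keep the Visit 1 CBC for eligibility.
- For subjects with no day 0 value, including any already challenged, use the Visit 1 value, put the baseline value and lead time in the model, and report a sensitivity analysis without these subjects. This avoids pooling 4-day intervals with 9- to 32-day intervals without adjustment.

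**Cost.** About 3 ml of blood per subject, one venipuncture for those whose PBMCs were drawn at Visit 1, and short edits to Table I, the Visit 2 list and section 13.4.4. The downside is one small extra blood sample per subject.

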## **9. Mechanistic Assays**

Detailed methodology is available in the RO1 application.

1. **Nasal Scrapings.** Will be evaluated for gene expression by quantitative RT-PCR for epithelial-associated genes associated with induction of Th2 profile (IL-25, IL-33, TSLP, and chemokines) and genes involved in anti-viral immunity (IFN- $\alpha$ , IFN- $\beta$ , IFN- $\lambda$ , and IL-15).
2. **Nasal Secretions (and Sponge):** Will be evaluated for viral load by qPCR and protein expression of cytokine genes as described above for qPCR. In addition, this material will be used to evaluate its Th2 immune deviating propensity.
3. **Blood samples:** Will be obtained for absolute eosinophil count. PBMCs (50-ml) obtained on day -7 will be enriched from the blood sample and used to address presence of immune-deviating propensity of the nasal sponge-derived milieu. Briefly, CD14+ monocytes will be obtained at visit 1 and differentiated into mDC in the presence of GM-CSF and IL-4. After 4 days mDC will be pulsed with tetanus and other relevant antigens for 2 additional days. A blood sample (50-ml) will also be obtained on day 4 and enriched for CD3+ T lymphocytes. At

day 6 antigen-pulsed mDC will be allowed to interact with the CFSE-labeled CD3+ T cells from day 4 and co-cultured for 5 days in the presence or absence of the epithelial cell-derived supernatants. Parallel samples of CD3+ T cells will be directly stimulated with anti-CD3/anti-CD28 beads and co-cultured with or without nasal secretion samples. After 5 days intracellular cytokine staining will be performed and % of Th1 (IFN- $\gamma$ ) and Th2 (IL-4) positive T cells determined amongst the CFSElow T cells.

4. **Nasal biopsies:** Up to three biopsies will be obtained at day 4 dpi. These specimens will be evaluated via immunohistochemistry to determine % of cell infected with RV. In parallel samples, epithelial cells will be identified via staining with APC-conjugated EpCAM and cell death/apoptosis quantified amongst the EpCAM positive population via staining with Annexin V/PI.

